6.2 Mediators and mechanisms -- Specific Aim 2b

Specific Aim 2b. We will investigate mechanisms- linkage of communications between all sectors, environmental (school and home) remediation steps, daily participation in SBAT, care coordination contacts achieved, correct MDI technique. A schematic of the mechanisms appears in Figure 6a

Figure 6a. Conceptual Framework

The intervention will in theory improve school, primary care provider, and home targets via the mechanisms: PFT, exposure to triggers, adherence to medications, self-management knowledge, and connection to resources.

6.2.1 Goals of mediation analysis

Mediation analysis can help to understand the etiology and mechanisms of change that give rise to the observed improvements from the intervention. It can also support measurement of direct effects of the intervention (on outcome without having an effect on the mediator) and indirect effects of the intervention (which produce outcomes through the mediating factor). (MacKinnon 2007) A key constraint for longitudinal designs is that candidate "mediators" should follow the sequence in time of exposure \rightarrow mediator \rightarrow outcome. If a candidate "mediator" occurs or could occur after the measured outcome, we will not consider that candidate. If the candidate mediator occurs contemporaneously with the outcome, and if its measurement is of interest, we shall consider it as "surrogate outcome".

6.2.2 School-level factors

The Consolidated Framework for Implementation Research (CFIR)

CFIR is an effort to synthesize the frameworks in implementation science. The five major domains that comprise the CFIR include:

(1) intervention characteristics (i.e., the features of an intervention such as School Based Asthma Therapy; SBAT);

(2) outer setting (i.e., the economic, political, and social context within which a school exists);

(3) inner setting (i.e., the organizational setting - school);

(4) characteristics of individuals involved in implementation (e.g., nurses, teachers); and

(5) the implementation process. In our specific example, at the nurse level, low self-efficacy or lack of knowledge about best practices for managing asthma in schools may contribute to low implementation of best practices. At the inner setting, challenges regarding availability of resources (e.g., forms related to asthma treatment, asthma medication) and organizational support (e.g., support from front-desk staff and management) may be present. Outer setting barriers may include lack of uniform policies to support implementation. Intervention characteristics such as ease of use are also relevant

6.2.3 Candidate mediation measures

Table	6.2.3
-------	-------

Mediating Factors	HYPOTHESES	Associated Variables and Instruments for Mediating Factors
Patient-level factors		
SELF- MANAGEMENT KNOWLEDGE	H1: The intervention will lead to improved caregiver self-management, which in turn will lead to improved child outcomes.	Asthma Knowledge Quiz Score (pre- and post-intervention)
SELF- EFFICACY	H1: The intervention will increase caregivers' self-efficacy, which will then lead to better child outcomes	Child Risk Assessment Tool
ADHERENCE	H1: The intervention will lead to greater chances of a child's receiving controller medications at least 80% of school days, which in turn will lead to better outcomes	SBAT Weekly Progress Form
CONNECTION TO RESOURCES	H1: The intervention will lead to more families making connections with resources, which in turn will le d to better outcomes.	Baseline Visit Checklist; Home Visit Follow-Up Checklist; Follow-Up Visit Checklist 3, 6, Months; 12-Month Follow-Up Checklist
Asthma TRIGGERS	H1: The intervention will reduce the number of triggers in childrens' bedrooms, leading to improved child outcomes	Initial Home Environmental Assessment; Follow-Up Home Environmental Assessment
Pulmonary Function Tests (PFTs)	H1: Children in the A+S+ will have improved PFT's, which will lead to better child outcomes.	Measured by spirometry every 3 months.
CARE COORDINATION GOALS	H1: The intervention will lead to more families who reach 80% care coordination goals, which will lead to better child outcomes.	Caregiver Goal Tracking Tool

Mediating factors, continued)	HYPOTHESES	Associated levels for Mediating factors
School level factors		
IMPROVED KNOWLEDGE	The school intervention will lead to improved knowledge of FOR SCHOOL STAFF (SCHOOL ADMINISTRATION EDUCATION) AND STUDENTS (OPEN AIRWAYS), and then to better child outcomes.	Asthma 101 pre- and post-test scores OAS pre- and post-test scores
ADHERENCE	The school intervention will improve the quality of School Based Asthma Therapy, and in turn to better child outcomes.	Number of days school open
COMPLETED MED1 FORMS	The school intervention will lead to more ACCURATE PRESCRIPTIONS IN SCHOOL and in turn to better outcomes.	School Nurse Baseline Checklist; School Nurse Follow-Up Checklist
IMPROVED PRIMARY CARE- SCHOOL COMMUNICATION	The school intervention will lead to improve communication between school and primary care clinicians (HOW MEASURED?) and then to better child outcomes.	School Nurse Baseline Checklist; School Nurse Follow-Up Checklist

6.2.4 Mediation models

This aim explores potential mediating variables (M) on the effect of the intervention (A=navigator; S=School) on student/patient outcomes (Y) with a goal of understanding which components of the intervention, and one or more dimensions of the intervention, proves to be ineffective, then the mediation can help to identify the reasons. Mediation analysis requires many and much stronger assumptions. We shall follow the counterfactual approach (Valeri 2013) to mediation to take advantage of recent statistical developments in causal inference (Lynch 2008; MacKinnon 2007; Bind 2016; Ten Have and Joffe 2012; Imai Keele and Tingley 2010; Preacher 2015; VanderWeele 2015; VanderWeele 2016). Because children are not randomized to levels of M, and to avoid the resulting potential bias, we will adopt two approaches: (1) Marginal structural models, in which mediator variables are modeled as functions of baseline covariates, have been developed for parametric estimation of direct and indirect effects without the severe assumptions of prior methods (Preacher 2011; Petersen 2006; Sobel 2008; VanderWeele 2009); (2) Simulation-based methods (Imai 2010) offer practical alternatives. These methods apply to clustered designs as well as traditional randomized designs (Stapleton, 2015; Ten Have, 2004; VanderWeele 2010). Using the nomenclature of recent reviews, the school intervention of our factorial design is 2-1-1, in which the intervention applies at level 2 (schools) and mediators and outcomes are measured at level 1 (child; Talloen 2016). Using these methods, we can decompose total intervention effect into the two components: natural direct effect (NDE= the effect of the intervention on child outcomes not mediated), and the natural indirect effect (NIE= the component of the intervention that seems to proceed through the measured mechanisms). As such, Total effect = NDE+ NIE (Peterson 2006; VanderWeele 2015). Within this framework, we can also estimate effects of multiple correlated mediators ((VanderWeele and Vansteelandt 2014)

6.2.5 Assumptions behind mediation models

Six assumptions must be satisfied for causal inferences for mediation and unbiased estimation of direct and indirect effects: (1) no $A \rightarrow Y$ and (2) no $A \rightarrow M$ confounding. These two assumptions will be met via design (randomization) and careful control of child-level covariates. Additional assumptions include: (3) no $M \rightarrow Y$ confounding, and (4) no $M \rightarrow Y$ confounder that is affected by A (exposure). Although these last two assumptions are not required for estimates of overall effects of the intervention ($A \rightarrow Y$), they are essential for estimating direct/indirect effects even with randomized A and S. For that reason, our design will collect data on possible confounders: grade level, child gender, and comorbidities

Two additional assumptions are noninterference at both the individual and school levels (also called *no spillover effects*). To limit noninterference at the school level (assumption 5: intervention at one school cannot influence the outcome at another (Sobel 2006)), we shall instruct each school to work alone and not to contact or share ideas with other schools. Noninterference at the child level (assumption 6) will require that children not share with each other their interactions with and information from navigators to lead to interference in the M \rightarrow Y relationship. Thus, we anticipate good compliance with key assumptions for unbiased mediation analysis.

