### 4.2 Study Treatment Phase

### 4.2.1 Study Visit 1 (Enrollment)

All study participants will complete the following:

- Consent/Assent
- Baseline Questionnaire
- Clinical and vital sign measurements of child [weight, height, BMI, blood pressure, pulse, temperature, pulse oximetry (SpO2)]
- Pulmonary function test (spirometry) with child if not obtained from medical record
- 2-week parental recall of symptoms, school absences, and work days missed
- Asthma Control Questionnaire
- Child Asthma Risk Assessment Tool (CARAT)
- Caregiver's Quality of Life Questionnaire
- Caregiver Needs Assessment
- Cost Analysis Parent Questionnaire
- Observe MDI technique and complete MDI Checklist
- Assess possible adverse events from date of enrollment

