## 5.3 Screening and Monitoring Evaluations and Measurements

#### 5.3.1 Medical Record Review

The following variables will be abstracted from the medical chart.

• Date of birth

- Weight
- Height
- Blood pressure
- Pulse
- Temperature
- SpO2 (Pulse Oximetry)
- Zip code of residence
- Gender
- Race/Ethnicity
- BMI
- Pulmonary function test results
- Asthma-related healthcare utilization (hospital, emergency, urgent care visits)

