5.1.2 Measuring outcomes over time - irregular measurement times

Longitudinal model

Although the protocol calls for regular measurement times (Juniper's **Asthma Control Questionnaire** is a validated survey and will be administered by the CHW at baseline, 3 months, 6 months, 9 months and 12 months), in all likelihood these measurements will have the following characteristics. (1) They will not be administered at 3,6, 9 and 12 months. For some the schedule will lag. (2) Some children will miss one or more of these measurements.

Although some RCTs assume that measurements occur at the protocol-defined time, even when they do not, there is no reason for, and we shall deliberately avoid, that ad hoc practice.

We shall model the time of each measurement as the number of months (including factional amounts) from date of randomization. Time we shall model flexibly with splines. [Here we can use cubic splines as needed).

Choices for knots. We shall assume knots at time 3, 6 and 9 months, the intended dates of measurements.

With time measured flexibly, and with a statistical model that includes time by treatment (4 level) interactions, the spline model will allow for estimate of differences (or ratios) of outcomes at any point along the time (x) axis by treatment group.

Covariates -- selection and balancing

In theory randomization at the child level should balance on observed and unobserved factors. With children spread over 36 schools, and with chance differences across school, imbalances in child characteristics are possible at the school level but are not likely at the treatment assignment level (the four cells a, b, c and d). In addition, dropout can undermine the balance achieved in theory and in practice by randomization.

Key child-level covariates appear in Table 5.1.2.

Table 5.1.2 Covariates – baseline descriptions

Child level factors	Units of measurement or categories
AGE	Subgroups: 5-11; 12-13
GENDER	Male Female
Body mass index (weight in kg) (height in cm)	Collected and/or calculated by age-sex standardized percentile and/or z score. Both percentile and z will be used
HOUSEHOLD CHARACTERISTICS (descriptive only)	 (1) Single Parent/Caregiver vs Multiple Caregivers (2) Number of Adults in household (3) Number of Children in Household
Home environment	Number of bedrooms
Smoking	Smokers or none in home
Caregiver Education Highest level achieved by primary caregiver	Less than HS HS+ Graduate Level
Baseline Healthcare utilization	

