6.2.6 Sensitivity analyses

Sensitivity analyses are absolutely essential for mediation analysis to assess the possible effects of confounding and interference. (1) For estimating the $A \rightarrow Y$ intervention effect, we shall use simulations to estimate how influential a confounder would need to be to produce a true $A \rightarrow Y$ association of zero, or to lead to a confidence interval that includes the null (non-significant result). (2) To examine sensitivity to violations of assumptions #3, #4 (no $M \rightarrow Y$ confounding) we shall assess how strong an unobserved confounder (or confounders) would need to be in order to: (a) eliminate (reduce to zero) the estimate for a direct effect, and (b) render non-significant that estimate. Methods are described by Imai (Statistical Sci 2010), VanderWeele (2016), VanderWeele (2015) and Ding (2016a; 2016b). Our team of investigators will continuously monitor emerging statistical methodological on mediation in complex randomized designs.

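### The only mediator-outcome confounders named for Aim 2b leave out baseline asthma control, prior-year utilisation and the available baseline mediator values, so indirect effects are at risk of confounding by severity

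*SAP*

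**What the plan says.** SAP 6.2.5 lists the assumptions behind the mediation analysis. On the two that concern confounding between mediator and outcome, it says that "they are essential for estimating direct/indirect effects even with randomized A and S", and it responds that "our design will collect data on possible confounders: grade level, child gender, and comorbidities".

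Four other places bear on covariate control:

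- SAP 6.2.5, on confounding of the intervention with the outcome or the mediator: "These two assumptions will be met via design (randomization) and careful control of child-level covariates".
- SAP 6.2.4 describes marginal structural models "in which mediator variables are modeled as functions of baseline covariates", without listing those covariates.
- SAP 5.1.2 states "Key child-level covariates appear in Table 5.1.2". That table holds prior-year steroid courses, ED visits and inpatient visits, but the SAP does not tie it to the mediation models.
- SAP 6.2.6 plans a sensitivity analysis: "we shall assess how strong an unobserved confounder (or confounders) would need to be in order to" remove the direct effect or its statistical significance.

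Protocol 4.2.1 gives the enrolment measures for all participants. They include the ACQ, spirometry, CARAT and the inhaler item "Observe MDI technique and complete MDI Checklist".

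**The concern.** Children are randomised to the interventions but not to levels of a mediator. A child's disease severity at entry can plausibly affect lung function, inhaler technique and adherence, and also later asthma control. If severity is left out of the models, part of that shared dependence is attributed to the mediator.

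The SAP itself treats entry severity as relevant to outcome. Table 6.1b hypothesises that baseline control and prior-year steroid courses predict response in asthma control at 12 months. Neither is among the confounders named in 6.2.5.

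At stake is the reading of Aim 2b, that is, which components of the programme appear to work and by what route. The comparisons of randomised groups do not depend on it.

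**Working it through.** **1. Does other SAP text fill the gap?**

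| Text | Why it does not settle the mediator-outcome set |
|---|---|
| SAP 6.2.5, control of child-level covariates | Tied to the first two assumptions, not to the mediator-outcome ones |
| SAP 6.2.4, baseline covariates | Not enumerated |
| SAP 5.1.2, treatment assignment model | Covariates enter only if unbalanced across the four groups; balance across groups does not remove mediator-outcome confounding |
| SAP 6.2.6, sensitivity analysis | Addresses unobserved confounders and names only the direct effect |

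**2. Which omitted variables are available?**

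| Variable | Baseline in all arms? | Source |
|---|---|---|
| ACQ | Yes | Protocol 4.2.1; SAP Table 5.1.1 |
| Prior-year ED, inpatient, steroid counts | Yes | SAP Table 5.1.2 |
| Spirometry | Yes | Protocol 4.2.1, 5.1 |
| MDI technique | Yes | Protocol 4.2.1 |
| CARAT (self-efficacy, SAP Table 6.2.3) | Yes | Protocol 4.2.1 |
| Asthma knowledge quiz | No: starts at Home Visit 1, which controls do not receive | Protocol 3.1, 4.3.2, 5.1 |
| Home triggers | No: home visits only | Protocol 5.1 |
| SBAT adherence | No pre-intervention value | SAP Table 6.2.3 |

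**3. The SAP's own mediation figures (SAP 6.3).** These supply the path sizes used in step 4.

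- Design effect: 600/23 = 26.1 children per school, and 1 + 0.06 x 25.1 = 2.51, matching the stated value of about 2.5.
- Child-level intervention to mediator at 0.25 SD, 300 per arm: 0.25 x sqrt(150) - 1.96 = 1.10, power 0.865.
- Mediator to outcome at 0.25: 0.25 x sqrt(600) - 1.96 = 4.16, power about 1.00.
- Joint power is about 0.86, consistent with the stated figure above 0.8.

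The SAP's figures reproduce, but power says nothing about bias.

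**4. Illustration of the bias.** Let U be baseline asthma status, with U, M and Y standardised and scored so that higher is better. Let a be the effect of the intervention on the mediator, b the effect of the mediator on the outcome, r the within-arm correlation of M with U, and g the effect of U on Y. In a linear model:

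- True indirect effect = a x b = 0.25 x 0.25 = 0.0625.
- Indirect effect without U = a x (b + r x g).
- Relative bias = r x g / b.

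The values a = b = 0.25 come from SAP 6.3. **The values of r and g are assumptions; the documents give neither.**

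| r | g | Indirect effect without U | Relative bias |
|---|---|---|---|
| -0.2 | 0.5 | 0.25 x (0.25 - 0.10) = 0.0375 | -40% |
| -0.2 | 0.1 | 0.25 x (0.25 - 0.02) = 0.0575 | -8% |
| 0 | any | 0.0625 | 0% |
| 0.1 | 0.1 | 0.25 x (0.25 + 0.01) = 0.0650 | +4% |
| 0.2 | 0.3 | 0.25 x (0.25 + 0.06) = 0.0775 | +24% |
| 0.3 | 0.5 | 0.25 x (0.25 + 0.15) = 0.1000 | +60% |

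A simulation with 2,000,000 children per setting agreed with the formula (for example 0.0374 at r = -0.2, g = 0.5, and 0.0999 at r = 0.3, g = 0.5). Including U returned 0.0622 to 0.0628 in every setting.

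**5. Outcome scale.** Protocol 6.3.2 defines the endpoint as change from Visit 1 to Visit 5. If U is the baseline ACQ and SDs are equal, the coefficient on U for change is g - 1. With g = 0.4 to 0.5 that is -0.6 to -0.5, so the direction of the bias reverses for a given r. The range in step 4 is therefore an illustration on the level scale, not a bound.

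**The case against.** The strongest reply is that the quoted sentence is about data collection and concerns possible confounders. It does not declare a model. The baseline covariates of SAP 6.2.4 could include severity, and Table 5.1.2 already lists utilisation counts. The SAP also plans a sensitivity analysis for exactly these assumptions. The aim is exploratory, it is Bonferroni-adjusted under SAP 9.1, and SAP 9.2 expects it very likely to fail for lack of numbers.

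Much of this stands, and it rules out several stronger readings:

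- A reader might infer that the indirect effects are confounded, or inflated, by severity. The documents do not show this. Analysts are not confined to three variables, and the sign depends on quantities not given. If sicker children adhere more, for instance, an indirect effect on the level scale could be masked.
- A reader might infer that baseline values of all mediators are already held. Only spirometry, MDI technique and CARAT have them in every arm.
- A reader might infer that grade level and comorbidities are not collected. They are absent from Table 5.1.2 and from the list introduced by "The following variables will be abstracted from the medical chart" in Protocol 5.3.1. The baseline questionnaire and intake survey are not shown, so this cannot be concluded.
- A reader might link the SAP's expectation of good compliance with its assumptions to the three-variable list. That sentence closes the paragraph on noninterference, so the link is only an inference.

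The reply does not remove the gap. The only set named for an assumption that the SAP calls essential omits measured severity. A sensitivity analysis for unobserved confounders does not replace adjustment for observed ones. Low power does not reduce bias.

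**Conclusion.** The point holds as a risk. If Aim 2b is adjusted only for the three named variables, measured baseline severity is left as a possible confounder of the indirect effects. Sign and size are unknown. The illustrative range of about -40% to +60% rests on linear models, a = b = 0.25 SD, r from -0.2 to 0.3, g from 0.1 to 0.5 and an outcome on the level scale. It is zero if severity is unrelated to the mediator.

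The change is worth making because the data are already held. It concerns the exploratory mediation aim only and does not touch the primary analysis.

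**What to change.** Amend SAP 6.2.4 to 6.2.6 as follows.

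1. State one adjustment set for the mediator models, the outcome models and the marginal structural model weights: baseline ACQ; prior-year ED, inpatient and oral steroid counts; age; sex; caregiver education; smoking in the home; clinic; and the baseline value of the mediator where it is measured in all arms (spirometry, MDI checklist, CARAT).
2. State that no baseline mediator value is available in all arms for the knowledge quiz, home triggers or SBAT adherence, so those analyses carry a weaker adjustment.
3. Handle school by a random effect or cluster-robust errors. Fixed school terms would be collinear with the school-randomised intervention and would absorb its effect.
4. Extend the SAP 6.2.6 sensitivity analysis to the indirect effect: how strong an unobserved confounder would have to be to bring it to zero or make it non-significant.

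The cost is SAP wording, with no new data. Because SAP 9.1 classes contrasts added after the SAP as exploratory, the set should be fixed in a dated amendment before the mediation outcomes are examined.

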6.2.6 Sensitivity analyses

Sensitivity analyses are absolutely essential for mediation analysis to assess the possible effects of confounding and interference. (1) For estimating the $A \rightarrow Y$ intervention effect, we shall use simulations to estimate how influential a confounder would need to be to produce a true $A \rightarrow Y$ association of zero, or to lead to a confidence interval that includes the null (non-significant result). (2) To examine sensitivity to violations of assumptions #3, #4 (no $M \rightarrow Y$ confounding) we shall assess how strong an unobserved confounder (or confounders) would need to be in order to: (a) eliminate (reduce to zero) the estimate for a direct effect, and (b) render non-significant that estimate. Methods are described by Imai (Statistical Sci 2010), VanderWeele (2016), VanderWeele (2015) and Ding (2016a; 2016b). Our team of investigators will continuously monitor emerging statistical methodological on mediation in complex randomized designs.

6.2.7 Statistical software

Statistical software for mediation continues to develop. Standard packages for both estimation and for sensitivity analyses are now available in Stata v 14.1 (Hicks 2011) and R (Tingley 2015; 2014) for the implementation of the methods of Imai (2010). Extensive macros in SAS for parametric methods are implemented by Ding and VanderWeele (2016). Stata's "gformula" package also

estimates natural direct and indirect effects (Daniel 2011) via simulations and this approach continues to find applications for mediation analysis (Wang 2015). The R package program 'medflex' supports mediation analysis to estimate natural effects. (Steen 2015)

To determine whether implementation fidelity and participant engagement are associated with outcomes, we propose to describe the impact of these factors on the outcomes in the intervention schools, with special attention to variation in outcomes across schools. These associations will not benefit from randomization (fidelity and engagement are post randomization interim process endpoints). For that reason, our assessments will be largely descriptive and qualitative, and will include follow-up contacts with the schools where school-level outcomes do not coincide with measured fidelity and engagement.

